6.2 Method and Timing

The assessments, as described in section 6.1, will occur as follows:

I. Physical Examination

The assessment will occur at screening. The information will be recorded in the appropriate CRF.

II. Clinical Laboratory Evaluations:

The assessment will occur upon admission to the hospital as well as at day 14. Additional laboratory tests or timing may be ordered as deemed necessary by the PI.

III. Adverse Events:

Adverse events will be assessed daily during the 28 day duration of the trial. The information will be recorded in the appropriate CRF.

The methods employed for completing assessments are described in section 6.1

6.3 Adverse Events

6.3.1 Definition of Adverse Event (AE)

AE means any medical event associated with the use of an intervention, whether or not considered intervention-related. An AE can be any unfavorable and unintended sign (including an abnormal laboratory finding), symptom, or disease temporally associated with the use of medicinal (investigational) product.

Any medical condition that is present at the time that the subject is screened will be considered as baseline and not reported as an AE. However, if the severity of any pre-existing medical condition increases, it should be recorded as an AE.

Given the nature of severity of the underlying illness, subjects will have many symptoms and abnormalities in vitals and laboratory. All Grade 3 and 4 AEs will be captured as AEs in this trial.

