4.1 Inclusion Criteria

1. Admitted to the hospital with symptoms of COVID-19
2. Male and females age ≥ 18 years old
3. Laboratory confirmed positive SARS-CoV-2 rtPCR test within 7 days prior to randomization or confirmed lung involvement by CT scan
4. Clinical status on the COVID-19 Ordinal Scale (defined in Section 5.1) of 3 to 6
5. Coagulation: INR $\leq 1.5 \times \text{ULN}$, and APTT $\leq 1.5 \times \text{ULN}$
6. Subject (or legally authorized representative) gives written informed consent prior to performing any study procedures
7. Subject (or legally authorized representative) agree that subject will not participate in another COVID-19 trial while participating in this study

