5.1 Efficacy Parameters

The following efficacy parameters will be assessed and recorded in the CRF.

I. COVID-19 Ordinal Scale:

The ordinal scale is an assessment of the clinical status of each subject. The scale is defined as follows:

- 8. Death;
- 7. Hospitalized, on invasive mechanical ventilation or ECMO;
- 6. Hospitalized, on non-invasive ventilation or high flow oxygen devices;
- 5. Hospitalized, requiring supplemental oxygen;

4. Hospitalized, not requiring supplemental oxygen- requiring ongoing medical care (COVID-19 related or otherwise);
3. Hospitalized, not requiring supplemental oxygen - no longer requires ongoing medical care;
2. Not hospitalized, limitation on activities;
1. Not hospitalized, no limitations on activities

II. Time to Recovery:

Time to recovery is defined as the first day on which the subject satisfies one of the following three categories from the ordinal scale (defined in Section 5.1): 3)

Hospitalized, not requiring supplemental oxygen - no longer requires ongoing medical care; 2) Not hospitalized, limitation on activities and/or requiring home oxygen; or 1) Not hospitalized, no limitations on activities.

III. “Multiple Combined Sensitive Outcome Detect Method” (combining items I and II):

1. (WHO COVID ORDINAL OUTCOMES SCALE):
 - a. 1 dia; b. 2 dias; c. 3 dias; d. 7 dias; e. 14 dias; f. 21 dias; g. 30 dias (cuja escala é plenamente contemplada por alguns dos desfechos descritos abaixo)
2. TEMPO ATÉ RECUPERAÇÃO – regressão aos níveis 1 e 2 da WHO COVID Ordinal Outcomes Scale (dias)
3. POSITIVIDADE DA rtPCR-SARS-CoV-2 a. 7 dias; b. 14 dias; c. 30 dias (%)
4. TEMPO ATÉ REMISSÃO DE CADA SINTOMA (dias)
5. TEMPO ATÉ REMISSÃO COMPLETA DOS SINTOMAS (dias)
6. TEMPO ATÉ RECUPERAÇÃO DA CAPACIDADE DE REALIZAÇÃO DE ATIVIDADES DIÁRIAS DEVIDO AOS SINTOMAS DE COVID-19 (Nível 1 da WHO COVID Ordinal Outcomes Scale) (dias)

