6.1 Safety Parameters

Safety parameters will be assessed as follows:

I. Physical Examination:

The PI will conduct a thorough physical examination during screening. The assessment will be recorded in the appropriate CRF.

II. Clinical Laboratory Evaluations:

The following tests will be conducted: WBC, differential, Hgb, PLT, creatinine, glucose, total bilirubin, AST, ALT and coagulation PT.

III. Adverse Events:

Safety will be assessed by summarizing the incidence and type of Adverse Events in a CRF form.

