6.3.2 Definition of Serious Adverse Event (SAE)

An SAE is defined as “An AE or suspected adverse reaction is considered serious if, in the view of either the investigator or the sponsor, it results in any of the following outcomes: Death, a life-threatening AE, inpatient hospitalization or prolongation of existing hospitalization, a persistent or significant incapacity or substantial disruption of the ability to conduct normal life functions, or a congenital anomaly/birth defect. Important medical events that may not result in death, be life-threatening, or require hospitalization may be considered serious when, based upon appropriate medical judgment, they may jeopardize the patient or subject and may require medical or surgical intervention to prevent one of the outcomes listed in this definition. Examples of such medical events include allergic bronchospasm requiring intensive treatment in an emergency room or at home, blood dyscrasias or convulsions that do not result in inpatient hospitalization, or the development of drug dependency or drug abuse.” “Life-threatening” refers to an AE that at occurrence represents an immediate risk of death to a subject. An event that may cause death if it occurs in a more severe form is not considered life-threatening. Similarly, a hospital admission for an elective procedure is not considered a SAE. All SAEs, as with any AE, will be assessed for severity and relationship to study intervention. All SAEs will be recorded on the appropriate SAE CRF. All SAEs will be followed through resolution or stabilization by a licensed study physician (for IND studies, a physician listed on the Form FDA 1572 as the site PI or Sub-Investigator). All SAEs will be reviewed and evaluated by DMID and will be sent to the SMC (for periodic review), and the IRB/IEC.

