--	--	-------------------------------------------------------------------------------------------------------------------------------------------------------------------------------------------------------------------------------------------------------------------------------------------------------------------------------------------------------------------------------------------------------------------------------------------------------------------------------------------------------------------------------------------------------------------------------------------------------------------------------------------------------------------------------------------------------------------------------------------------------------------------------------------------------------------------------------------------------------------------------------------------------------------------

3. General principles

As proposed in the final protocol	Done in the final statistical Plan	Rationale
Continuous variables will be expressed as median (interquartile range [IQR]) and categorical variables will be expressed as a number	Continuous variables were expressed as median (IQR) and categorical variables were expressed as a number and in a risk percentage.	Expression of the categorical variables only as a number is not sufficient to allow for calculation of risk ratios. Then, absolute risk ratios were calculated for primary (14-day Overall Recovery rate) and secondary outcomes (28-day recovery rate and 28-day all-cause mortality)
95% confidence intervals will be calculated for the primary outcome	95% confidence intervals will be calculated for the primary outcome, secondary outcomes and subgroup analysis.	All secondary outcomes expressed in ratios were reported along with the 95% confidence interval to allow for a better understanding of the effect sizes.
Group comparisons will be analyzed by the Wilcoxon rank sum test or χ^2 test	For all categorial effect sizes, hypothesis testing was performed with the χ^2 test, including risk ratios. 95% Confidence intervals were reported in results tables, for the primary endpoint Overall Recovery Ratio), along with the P value. For the Adverse AE table, P-values were included. Other outcomes described as median and IQR were compared with the Wilcoxon rank sum test.	The primary hypothesis testing previously stated was maintained. However, we explained in which cases the different tests were applied to increase transparency.

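### Worsening COVID-19 counts as an adverse event and the AE table carries P-values, so efficacy against worsening could offset toxicity in the pooled AE rows

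*Combined protocol and SAP*

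**What the plan says.** All references are to the final protocol (revision 8) and the final statistical plan appended to it.

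- **Entry.** Section 4.1 requires each subject to be "Admitted to the hospital with symptoms of COVID-19".
- **AE definition.** Section 6.3.1 first sets a baseline: "Any medical condition that is present at the time that the subject is screened will be considered as baseline and not reported as an AE". It continues: "However, if the severity of any pre-existing medical condition increases, it should be recorded as an AE". After noting that the illness itself will produce many abnormalities, it states: "All Grade 3 and 4 AEs will be captured as AEs in this trial".
- **SAE definition.** Section 6.3.2 lists among its qualifying outcomes "Death, a life-threatening AE, inpatient hospitalization or prolongation of existing hospitalization".
- **Efficacy scale.** Section 5.1 scores death as 8, "Hospitalized, on invasive mechanical ventilation or ECMO" as 7, and continued hospital stay in the lower hospital categories. Death by day 28 is also a secondary outcome.
- **Safety analysis.** Section 6.1: "Safety will be assessed by summarizing the incidence and type of Adverse Events in a CRF form". The final statistical plan, part 3 (General principles), in the row on group comparisons, adds: "For the Adverse AE table, P-values were included".
- **Attribution.** Section 6.3.6 has each event judged Related or Not Related. Section 6.3.8 records the association with the product and groups linked signs under one diagnosis. Neither section, nor the final plan, sets out an analysis by arm that uses these judgements.

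**The concern.** The same clinical course can enter the trial twice: as a poor efficacy score, and as an AE or SAE. When the AE table is then compared between arms with P-values, its pooled rows partly retest efficacy.

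This cuts two ways. If the drug prevents worsening, the active arm loses progression events, and events that the drug causes can fill the gap unnoticed. If it does not, progression events in both arms add noise and reduce the chance of seeing an excess. In either case a lower or equal all-event rate could be taken as reassurance about tolerability. Section 1 gives safety, alongside efficacy, as a purpose of the study.

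Some overlap of terms is plausible. Study 4 lists fatigue, decreased appetite, raised transaminases and anaemia, all of which can also accompany the illness. That table gives no grades. Study 3 did report Grade 3 or higher anaemia (7/40) and fatigue (5/40), although most of its Grade 3 or higher events were judged unrelated to the drug.

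**Working it through.** **No stated figure to reproduce.** The documents give no expected AE rate, no power for a safety comparison and no safety margin. Everything below illustrates the mechanism under stated assumptions.

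**Inputs from the documents.** 147 subjects per arm in each cohort, so 2 × 147 = 294 per arm with both cohorts pooled; two-sided 5% level; odds ratio 2.0 (section 7.2, planned for improvement on the ordinal scale).

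**Assumptions.** A proportion p of placebo subjects have a Grade 3-4 COVID-19 progression event, with p from 20% to 40%. An odds ratio of 2 applies to those events. A proportion t of active subjects without progression have a drug-caused event. There are no other background events.

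**Step 1: progression in the active arm.** Halving the odds gives p1 = p/(2 − p).

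**Step 2: toxicity that is exactly offset.** Solve p1 + (1 − p1)t = p. Then t = (p − p1)/(1 − p1) = p/2.

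| p (placebo) | p1 (active) | toxicity offset, t |
|---|---|---|
| 20% | 11.1% | 10% |
| 30% | 17.6% | 15% |
| 40% | 25.0% | 20% |

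**Step 3: one case as a table.** Take p = 30%, t = 5% and 294 per arm.

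- Placebo: 0.30 × 294 = 88 subjects with an event.
- Active: 0.1765 + 0.8235 × 0.05 = 0.218, and 0.218 × 294 = 64 subjects.
- 64/294 v 88/294: chi-square 5.11, P=0.024 (0.030 with continuity correction), in favour of the drug.
- Active subjects without progression who have a toxic event: 242 × 0.05 = 12, against 0 on placebo. If toxicity applies to all 294 subjects, the count is 15 v 0. An uncorrected chi-square gives P<0.001 for either count.

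**Step 4: no efficacy, dilution only.** Assume 40% progression in both arms, 10% other background events and 10% toxicity.

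- Progression counted: placebo 1 − 0.60 × 0.90 = 46.0%; active 1 − 0.60 × 0.90 × 0.90 = 51.4%.
- Progression kept apart: placebo 10%; active 1 − 0.90 × 0.90 = 19%.

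| Per arm | Power, progression counted | Power, progression apart |
|---|---|---|
| 147 | 15% | 59% |
| 294 | 26% | 87% |

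**Step 5: modest efficacy.** Use the inputs of step 4, but let the drug cut progression by a quarter (40% to 30%). The active rate is 1 − 0.70 × 0.90 × 0.90 = 43.3%, below the placebo 46.0% despite 10% toxicity. The chance of a significant excess on active is about 1% at 147 per arm and 0.4% at 294.

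**Does the relatedness flag isolate progression?** Under section 6.3.6 a temporal relationship alone is enough for Related, while an established alternative cause is enough for Not Related. COVID-19 worsening during dosing can satisfy both. The flag therefore does not sort progression from other events.

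**The case against.** Several points on the other side stand.

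- **Recording worsening as an AE is not in itself an error.** Section 6.3.1 defines AEs irrespective of cause. The gap is in the analysis.
- **A reader might infer that any efficacy lowers the AE rate.** The documents do not support that. Earlier discharge of subjects who never worsen need not change Grade 3-4 counts. The effect requires efficacy against worsening.
- **A reader might infer that toxicity would be hidden throughout the AE table.** That is also too strong. Section 6.1 plans incidence and type, and an event type distinct from COVID-19 would show in its own row. The plan does not say that a pooled total is the tested row.
- **The overlap with the scale is partial.** Score 6 is allowed at entry, so it is not always worsening.
- **The odds ratio is borrowed.** It was planned for ordinal improvement, with a day 14 primary endpoint, whereas AEs are collected to day 28. The event and toxicity rates are assumed.
- **Other safeguards exist.** Serious events are reviewed individually and reported outside any P-value, and sections 6.3.6 and 6.3.8 collect attribution and a diagnosis.

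These points narrow the concern without removing it. Attribution is collected but not tied to the table that carries P-values. Grouping signs under one diagnosis can also move a laboratory abnormality out of its own row and into a COVID-19 row.

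**Conclusion.** The point holds for pooled and overlapping rows: any AE, Grade 3-4, SAE and respiratory events. As written, COVID-19 worsening enters those rows and nothing in the final plan separates it before P-values are attached. Under the assumptions shown, toxicity of 10% to 20% among subjects without progression could leave overall rates equal, and 5% toxicity could accompany a nominally significant result in the drug's favour. Without efficacy, power to see an excess falls sharply.

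The direction follows from the definitions. The size rests on assumed event rates and on applying an odds ratio of 2 to progression events. Because the documents contain no AE results from this trial, they cannot show that toxicity was in fact hidden. This is a worthwhile, inexpensive improvement to the safety analysis.

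**What to change.** In section 6.3.8 and the final statistical plan:

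1. Have each AE classified, blind to arm, as COVID-19 progression or other. The final plan states that its changes were made during manuscript writing. If collection is closed, masked reviewers can classify from the diagnosis, dates and severity that section 6.3.8 already requires.
2. Report both classes by arm and by event type. For the other events, give risk differences with 95% confidence intervals.
3. Keep the all-event table beside them, and state that a lower all-event rate is not to be read as evidence of safety.
4. State which AE rows carry P-values.

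Section 3.6 ties discontinuation to the same SAEs and Grade 3-4 AEs, so it and the AE definition in 6.3.1 must be reconciled.

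The cost is one CRF field, or one masked review of recorded events, plus extra tables. The downside is that attribution is a judgement: liver or haematological toxicity could be put down to COVID-19. For that reason the all-event and by-type tables must stay.

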6.3.2 Definition of Serious Adverse Event (SAE)

An SAE is defined as “An AE or suspected adverse reaction is considered serious if, in the view of either the investigator or the sponsor, it results in any of the following outcomes: Death, a life-threatening AE, inpatient hospitalization or prolongation of existing hospitalization, a persistent or significant incapacity or substantial disruption of the ability to conduct normal life functions, or a congenital anomaly/birth defect. Important medical events that may not result in death, be life-threatening, or require hospitalization may be considered serious when, based upon appropriate medical judgment, they may jeopardize the patient or subject and may require medical or surgical intervention to prevent one of the outcomes listed in this definition. Examples of such medical events include allergic bronchospasm requiring intensive treatment in an emergency room or at home, blood dyscrasias or convulsions that do not result in inpatient hospitalization, or the development of drug dependency or drug abuse.” “Life-threatening” refers to an AE that at occurrence represents an immediate risk of death to a subject. An event that may cause death if it occurs in a more severe form is not considered life-threatening. Similarly, a hospital admission for an elective procedure is not considered a SAE. All SAEs, as with any AE, will be assessed for severity and relationship to study intervention. All SAEs will be recorded on the appropriate SAE CRF. All SAEs will be followed through resolution or stabilization by a licensed study physician (for IND studies, a physician listed on the Form FDA 1572 as the site PI or Sub-Investigator). All SAEs will be reviewed and evaluated by DMID and will be sent to the SMC (for periodic review), and the IRB/IEC.

6.3.3 Suspected Unexpected Serious Adverse Reactions (SUSAR)

A SUSAR is any SAE where a causal relationship with the study product is at least reasonably possible but is not listed in the Investigator Brochure (IB), Package Insert, and/or Summary of Product Characteristics.

6.3.4 Classification of an Adverse Event

The determination of seriousness, severity, and causality will be made by an on-site investigator who is qualified (licensed) to diagnose AE information, provide a medical evaluation of AEs, and classify AEs based upon medical judgment. This includes but is not limited to physicians, physician assistants, and nurse practitioners.

6.3.5 Severity of Adverse Events

All AEs and SAEs will be assessed for severity, according to the Division of AIDS (DAIDS) Table for Grading the Severity of Adult and Pediatric Adverse Events, version 2.1 (July 2017). For AEs not included in the protocol defined grading system, the following guidelines will be used to describe severity.

Mild (Grade 1): Events that are usually transient and may require only minimal or no treatment or therapeutic intervention and generally do not interfere with the subject's usual activities of daily living.

Moderate (Grade 2): Events that are usually alleviated with additional specific therapeutic intervention. The event interferes with usual activities of daily living, causing discomfort but poses no significant or permanent risk of harm to the research subject.

Severe (Grade 3): Events interrupt usual activities of daily living, or significantly affects clinical status, or may require intensive therapeutic intervention. Severe events are usually incapacitating.

Severe (Grade 4): Events that are potentially life threatening.

AEs characterized as intermittent require documentation of onset and duration of each episode. The start and stop Duration of each reported AE will be recorded on the appropriate CRF. Changes in the severity of an AE will be documented to allow an assessment of the duration of the event at each level of intensity.

6.3.6 Relationship to Study Intervention

For each reported adverse reaction, the PI or designee must assess the relationship of the event to the study product using the following guideline:

Related – The AE is known to occur with the study intervention, there is a reasonable possibility that the study intervention caused the AE, or there is a temporal relationship between the study intervention and event. Reasonable possibility means that there is evidence to suggest a causal relationship between the study intervention and the AE.

Not Related – There is not a reasonable possibility that the administration of the study intervention caused the event, there is no temporal relationship between the study intervention and event onset, or an alternate etiology has been established.

6.3.7 Time Period and Frequency for Event Assessment and Follow-Up

For this study, all Grade 3 and 4 AEs and all SAEs occurring from the time the informed consent is signed through the Day 28 (end of study) visit will be documented, recorded, and reported.

6.3.8 Investigators Reporting of AEs

Information on all AEs should be recorded on the appropriate CRF. All clearly related signs, symptoms, and results of diagnostic procedures performed because of an AE should be grouped together and recorded as a single diagnosis. If the AE is a laboratory abnormality that is part of a clinical condition or syndrome, it should be recorded as the syndrome or diagnosis rather than the individual laboratory abnormality. Each AE will also be described in terms of duration (start and stop date), severity, association with the study product, action(s) taken, and outcome.

6.3.9 Serious Adverse Event Reporting

6.3.9.1 Investigators Reporting of SAEs

Any AE that meets a protocol-defined criterion as a SAE must be submitted immediately (within 24 hours of site awareness) on an SAE form to the DMID Pharmacovigilance Group, at the following address:

DMID Pharmacovigilance Group
Clinical Research Operations and Management Support (CROMS)
[name]
[name]
SAE Hot Line: [name] (US) or [name] (outside US) SAE FAX
Number: [name] (US) or [name] (outside US) SAE Email Address:
[contact]

Other supporting documentation of the event may be requested by the DMID Pharmacovigilance Group and should be provided as soon as possible. The DMID Medical Monitor will review and assess the SAE for regulatory reporting and potential impact on study subject safety and protocol conduct. At any time after completion of the study, if the site PI or appropriate sub-investigator becomes aware of an SAE, the site PI or appropriate sub-investigator will report the event to the DMID Pharmacovigilance Group.

